3.4.3 Total dose determination

1. Total dose determination will depend on the currently accruing dose level
2. Starting dose level is based on current institution standards and retrospective reports from other institutions^{15,19}.

Table 1. Summary of dose levels to be tested.

Dose level	Total Dose (Gy)	Dose per Fraction (Gy)	Fraction Number	BED ₁₀ (Early Effects)	BED ₃ (Late Effects)
-1	27.5	5.5	5	44	78
0	30	6	5	49	90
1	32.5	6.5	5	55	103
2	35	7	5	60	117
3	37.5	7.5	5	66	131
4	40	8	5	69	147
SRS*	18-21 Gy	18-21 Gy	1	53-68	126-168

*for comparison only, single fraction SRS will not be used in this protocol

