3.4.4 Dose prescription and dosimetry requirements

1. Dose will be prescribed to the isodose line that encompasses the entirety of the PTV.
 1. If intensity modulated radiosurgery (IMRS) is utilized, standard prescription isodose is to 98% (range 95-100%)
 2. If dynamic conformal arcs (DCA) are utilized, standard prescription isodose is to 80% (range 70-90%).
 3. If gamma knife is utilized, standard prescription isodose is to 50%

2. Doses are specified such that at least 95% of the PTV shall receive 100% of the prescribed dose.
 3. Inhomogeneity within the PTV should be kept within $\pm 10\%$ of the prescribed dose, and the minimum dose PTV should be kept within 10% of the dose at the isocenter.
 4. The marginal dose and the 100% dose (isocenter dose) will be recorded for each patient.
 5. For quality control, representative isodose lines (eg. 20%, 40%, 60%, 80%, 90%) must be generated for each patient.
- Quality of PTV coverage will be categorized according to selected isodose line:
1. Total – selected isodose line completely encompasses the PTV
 2. Marginal – selected isodose line incompletely encompasses the PTV, but not by more than 10% of the PTV volume.
 3. Subtotal - selected isodose line incompletely encompasses the PTV, but by more than 10% of the PTV volume. This will not be accepted.
6. Conformality index requirements (ratio of prescription isodose volume to the target volume (PI/TV))
 1. Per protocol if between 1.0 and 2.0
 2. Acceptable variation if ≥ 0.9 but < 1.0 or > 2.0 but ≤ 3.5 .
 3. Unacceptable deviation if > 3.5 .

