3.4.6 Dose Limitation to Critical Structures

1. In addition to the above defined GTVs, CTVs and PTVs, both eyes, the lenses of both eyes, the optic nerves, the optic chiasm, the brainstem and the spinal cord and the whole brain and normal brain parenchyma will be contoured. Normal brain is defined as the whole brain minus the GTV. Dose-volume histograms will be generated and whole organ dose and maximum point dose will be recorded for each critical structure.
2. If the patient has received no prior cranial irradiation, the maximal point doses permissible to the structures from the current radiation therapy plan are listed below* (Table 2).

3. If the patient has received previous WBRT, the previous dose received to critical structures should be obtained or a representative dose distribution file should be simulated. This dose should then be converted to BED (assuming an alpha-beta ratio of 3 for late effects) and added to the BED to the critical structures from the current treatment plan. This sum BED must meet the cumulative dose constraint below[¶] (Table 2). No adjustments for time between previous radiation treatment will be made for the purpose of this protocol.
4. If a patient is recommended to receive whole brain radiation after completion of the study treatment, the constraints listed in Table 3 should be met during the whole brain radiation treatment. It is recommended that the 90% isodose volume from the hypofractionated radiosurgery treatment be created into an avoidance structure and constrained such that the maximum dose to this structure or the normal brain has a cumulative BED₃ of ≤ 150 (equivalent to max dose 15-18 Gy when delivered in 3-3.5 Gy per fraction).

Table 2. Normal Tissue Constraints for Hypofractionated Radiosurgery Treatment

Cumulative BED ₃	Volume	No Previous RT*	Previous RT [¶]
		Maximum Dose	Maximum Cumulative BED ₃
Brainstem	Max, $\leq 0.03\text{cc}$	26 Gy	90
Spinal Cord	Max, $\leq 0.03\text{cc}$	22 Gy	75
Eye (Globe), each	Max, $\leq 0.03\text{cc}$	20 Gy	66
Lens, each	Max, $\leq 0.03\text{cc}$	2.5	12
Optic Nerve, each	Max, $\leq 0.03\text{cc}$	26 Gy	90
Optic Chiasm	Max, $\leq 0.03\text{cc}$	26 Gy	90
Normal Brain	Modal	20 Gy	15 Gy
Normal Brain	$\leq 23\text{ cc}$	4 Gy/fraction	4Gy/fraction

Table 3: Constraints for Whole Brain Radiation following hypofractionated radiosurgery

Cumulative BED ₃	Volume	WBRT after study treatment
		Maximum Cumulative BED ₃
Brainstem	Max, $\leq 0.03\text{cc}$	90

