Spinal Cord	Max, $\leq 0.03\text{cc}$	75
Eye (Globe), each	Max, $\leq 0.03\text{cc}$	66
Lens, each	Max, $\leq 0.03\text{cc}$	12
Optic Nerve, each	Max, $\leq 0.03\text{cc}$	90
Optic Chiasm	Max, $\leq 0.03\text{cc}$	90
Dose within 90% isodose line from study treatment or within normal brain	Max, $\leq 0.03\text{cc}$	150

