3.8.1 Neurologic Toxicity Assessment

1. Neurologic/CNS Toxicity will be graded according to the Common Toxicity Criteria for Adverse Events (CTCAE) version 4.03 (**Appendix B**).
2. Toxicity assessment will be made during treatment at weekly MD visits and at each follow up (1 month and 4 months after completion of radiation therapy, and every 3 months thereafter). A plus or minus 3 week window will be allowed for follow-up assessments.
3. Toxicity will be classified as immediate (within 24 hours of treatment), acute (within 4 months), or chronic (more than 4 months) based on timing after SRS.
4. Toxicities of any grade should be recorded by the radiation oncology staff on the study specific case report form at the prespecified assessment time points. All \geq grade 3 nervous system toxicity will be reported to the study principle investigator (PI).
5. Toxicities attributed to chemotherapy recorded by medical oncology staff will not be captured as study related AEs.
6. Attribution will initially be scored by the study investigators on the case report form and/or the physician seeing the patient in follow-up visit on a five point scale: 5=definitely caused by radiation treatment, 4= probably caused by radiation treatment, 3=possibly caused by radiation treatment, 2= probably not caused by radiation treatment, 1= not due to radiation treatment. Attribution will be reviewed by the PI and co-investigators. Any \geq grade 3 CNS toxicity with attribution ≥ 3 will be considered at DLT and will be reported to the DSMC. If a grade 3 CNS toxicity occurs after the patients is considered off study this will not be considered a DLT.
7. Any grade 5 toxicity will halt the study for review by the DSMC and IRB.
8. Maximal Tolerated Dose (MTD)
The MTD will be defined as the highest dose level where a grade 3 or greater with an attribution score of ≥ 3 develops in ≤ 2 of 6 patients in a dose group within 4 months of the treatment.
9. Laboratory values are not required for this protocol and will not be collected.

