4.6 Criteria for patient to be considered off study

- 4.6.1 Patient death.
- 4.6.2 Patient undergoes whole brain radiation therapy. However, we will continue to follow the patient after whole brain radiation therapy to document whether there are any enhanced toxicities with the combination of the study treatment and whole brain radiotherapy.
- 4.6.3 Patient request to come off study.

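### Section 3.4.6 item 4 gives one WBRT dose, 15-18 Gy, as the equivalent of a cumulative BED3 of 150 at every dose level; even with the study maximum at prescription dose it totals 161-170 at level 3 and 177-186 at level 4.

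*Combined protocol and SAP*

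**What the plan says.** Section 3.4.6 item 4 covers patients who are advised to have WBRT after study treatment. It says Table 3 should be met. It recommends turning the 90% isodose volume of the study plan into an avoidance structure, "constrained such that the maximum dose to this structure or the normal brain has a cumulative" BED3 of at most 150. A parenthesis then describes that limit as "equivalent to max dose 15-18 Gy when delivered in 3-3.5 Gy per fraction".

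The last row of Table 3, "Dose within 90% isodose line from study treatment or within normal brain", repeats the limit of 150 as a maximum (0.03 cc or less). Neither place ties 15-18 Gy to a dose level.

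Table 1 ("Summary of dose levels to be tested") lists six levels, with BED3 of 78, 90, 103, 117, 131 and 147 for levels -1 to 4.

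Section 3.4.4 item 1 sets the prescription isodose by technique. For intensity-modulated radiosurgery the "standard prescription isodose is to 98"% (range 95-100%). For dynamic conformal arcs it is 80% (range 70-90%), and for Gamma Knife 50%.

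**The concern.** A cumulative limit leaves a remainder that shrinks as the first course grows. Table 1 runs from BED3 78 to 147, so no single WBRT dose can be equivalent to a total of 150 at all six levels.

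The parenthesis is the only figure in Gy that the protocol offers for this volume during later WBRT, so a planner may reach for it. At the highest levels, doing so breaks the limit it is meant to express.

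The patients concerned have left the trial's DLT safeguard. WBRT takes them off study (section 4.6.2), and section 3.8.1 item 6 says: "If a grade 3 CNS toxicity occurs after the patients is considered off study this will not be considered a DLT". The protocol does keep an interest in them, since section 4.6.2 adds that "we will continue to follow the patient after whole brain radiation therapy to document whether there are any enhanced toxicities". A sound dose limit matters for these patients even though their later events do not enter dose escalation.

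**Working it through.** **Inputs.** The limit is cumulative BED3 150, on the maximum dose (3.4.6 item 4, Table 3). The alpha/beta ratio is 3 Gy (3.4.6 item 3). The study course is 5 fractions of 5.5, 6, 6.5, 7, 7.5 or 8 Gy (Table 1). The gloss is 15-18 Gy at 3-3.5 Gy per fraction.

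**Formula.** BED3 = D(1 + d/3), with D the total dose and d the dose per fraction.

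**Reproducing Table 1.** For levels -1 to 4 the formula gives 77.9, 90.0, 102.9, 116.7, 131.25 and 146.7, which agree with the printed BED3 values after rounding.

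**The gloss in BED3.** 15 × (1 + 3/3) = 30.0; 18 × (1 + 3/3) = 36.0; 15 × (1 + 3.5/3) = 32.5; 18 × (1 + 3.5/3) = 39.0. The range is 30-39.

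**Case A: study maximum equal to prescription.** This is the smallest maximum consistent with 3.4.4 item 2, which requires at least 95% of the PTV to receive the full prescribed dose.

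| Level | Study BED3 | 150 minus study | Total with the gloss |
|---|---|---|---|
| -1 | 77.9 | 72.1 | 108-117 |
| 0 | 90.0 | 60.0 | 120-129 |
| 1 | 102.9 | 47.1 | 133-142 |
| 2 | 116.7 | 33.3 | 147-156 |
| 3 | 131.25 | 18.75 | 161-170 |
| 4 | 146.7 | 3.3 | 177-186 |

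Only level 2 spans 150. There the remainder converts to 33.3/2 = 16.7 Gy at 3 Gy per fraction, or 33.3/2.167 = 15.4 Gy at 3.5, so the plan's own figure is reproduced at that level. Level 3 exceeds the limit by 11-20 units and level 4 by 27-36. At level 4 a single 3 Gy fraction to the volume is already too much: 146.7 + 3 × (1 + 3/3) = 152.7.

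**Case B: study maximum above prescription.** If the maximum is prescription divided by the prescription isodose:

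- 98%, level 4: 40/0.98 = 40.8 Gy, or 8.16 Gy per fraction; BED3 151.9 before any WBRT.
- 80%, level -1: 34.4 Gy, BED3 113. Level 0: 37.5 Gy, BED3 131. Level 1: 40.6 Gy, BED3 151, so the limit is spent before any WBRT.
- 50%, level -1: 55 Gy at 11 Gy per fraction; 55 × (1 + 11/3) = 257, already over the limit at the lowest level.

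At 110% of prescription (the upper inhomogeneity bound in 3.4.4 item 3), level 1 has study BED3 121.0, and the gloss brings the total to 151-160.

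**Case C: the lenient reading.** Suppose the study contribution is the dose at the edge of the 90% volume, taken as 90% of prescription. Level 3 is then 109.7 and totals 140-149, which passes. Level 4 is 122.4 and totals 152-161, which still fails.

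**The case against.** **The governing limit is right.** Table 3 states 150, and the 15-18 Gy is a parenthesis inside a recommendation. Table 1 prints the study BED3 and item 3 states the alpha/beta ratio, so a planner who does the sum for each patient is not misled. The figure may be a worked example for level 2 that lost its label. All of this stands and limits the severity. It does not make the word equivalent correct, and nothing elsewhere in the protocol corrects it.

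**The excess depends on how dose is counted.** On Case C, level 3 passes. But the limit is on the maximum in the volume, and that is at least the prescription dose. A spared structure inside a whole-brain plan would also receive less than 3 Gy per fraction. If the course had 10 fractions (an assumption; the documents give no number), 15-18 Gy to the structure is 15 × 1.5 = 22.5 to 18 × 1.6 = 28.8. Level 3 then totals 154-160 and level 4 169-175, both still over 150.

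**Two stronger readings do not hold.** A reader might infer from Case A that 15-18 Gy is needlessly restrictive at levels -1 to 1. That requires the study maximum to equal prescription, and 3.4.4 permits prescription isodoses at which it does not: at 80% the remainder at level 0 is 150 - 131.25 = 18.75, not 60. The inhomogeneity clause in 3.4.4 item 3 sits awkwardly with 80% and 50% prescriptions, so the documents do not settle which maximum applies. A reader might also infer bias in the MTD. Later WBRT is off study and subsequent grade 3 CNS toxicity is not a DLT, so the documents give no route from this parenthesis to the MTD.

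**Conclusion.** The parenthesis is wrong as written. One WBRT dose with no level attached cannot be equivalent to a cumulative BED3 of 150 when the study course alone contributes 78 to 147. With the study maximum at prescription, it matches level 2 only and overshoots by 11-20 units at level 3 and 27-36 at level 4. Any higher maximum makes the overshoot larger and extends it to lower levels. Level 4 exceeds the limit under every reading tried; level 3 passes only on the lenient one.

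The result rests on the protocol's own BED3 model and on simple addition of the two courses. Item 3 makes no time adjustment for prior radiotherapy; item 4 is read in the same way.

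Severity is minor to moderate. The figure concerns patient safety and would breach a stated limit if used, but Table 3 governs, the treatment is off study, levels 3 and 4 may not be reached, and the trial's primary result is untouched.

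**What to change.** In 3.4.6 item 4, replace the parenthesis with: the WBRT dose D actually received by this structure, at d Gy per fraction to the structure, must satisfy D(1 + d/3) ≤ 150 minus the BED3 of the maximum dose in that patient's study plan. Add that at level 4 (BED3 147 at prescription) not even one 3 Gy fraction to this volume meets 150. At minimum, delete the parenthesis and let Table 3 stand alone.

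A table of allowable WBRT doses by level, computed at prescription dose, should not be printed. At level 0 it would show 60/2 = 30 Gy at 3 Gy per fraction, whereas an 80% isodose plan leaves 18.75/2 = 9.4 Gy.

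The cost is one sentence. The limit, dose levels, eligibility and sample size stay as they are. No new data are needed: "The marginal dose and the 100% dose (isocenter dose) will be recorded for each patient", and 3.4.6 item 1 already calls for dose-volume histograms and maximum point doses. The correction does make plain that at the upper levels, or with a low prescription isodose, later WBRT may have to spare the treated volume almost wholly, or that no dose to it meets 150. That follows from the protocol's own limit. If the sponsor does not intend it, the 150 itself needs a stated change.

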3.5 Drug Therapy

No medications will be administered as part of the protocol. Patients may receive systemic chemotherapy or other drugs at the discretion of the treating physician.

3.6 Surgery

Patients may be status post resection of solitary brain metastases as per neurosurgery before trial registration. No surgical procedures will be performed as part of this protocol.

3.7 Other Therapies

Not applicable to this protocol.

3.8 Patient Assessments

See appendix A for assessment timeline

3.8.1 Neurologic Toxicity Assessment

1. Neurologic/CNS Toxicity will be graded according to the Common Toxicity Criteria for Adverse Events (CTCAE) version 4.03 (**Appendix B**).
2. Toxicity assessment will be made during treatment at weekly MD visits and at each follow up (1 month and 4 months after completion of radiation therapy, and every 3 months thereafter). A plus or minus 3 week window will be allowed for follow-up assessments.
3. Toxicity will be classified as immediate (within 24 hours of treatment), acute (within 4 months), or chronic (more than 4 months) based on timing after SRS.
4. Toxicities of any grade should be recorded by the radiation oncology staff on the study specific case report form at the prespecified assessment time points. All \geq grade 3 nervous system toxicity will be reported to the study principle investigator (PI).
5. Toxicities attributed to chemotherapy recorded by medical oncology staff will not be captured as study related AEs.
6. Attribution will initially be scored by the study investigators on the case report form and/or the physician seeing the patient in follow-up visit on a five point scale: 5=definitely caused by radiation treatment, 4= probably caused by radiation treatment, 3=possibly caused by radiation treatment, 2= probably not caused by radiation treatment, 1= not due to radiation treatment. Attribution will be reviewed by the PI and co-investigators. Any \geq grade 3 CNS toxicity with attribution ≥ 3 will be considered at DLT and will be reported to the DSMC. If a grade 3 CNS toxicity occurs after the patients is considered off study this will not be considered a DLT.
7. Any grade 5 toxicity will halt the study for review by the DSMC and IRB.
8. Maximal Tolerated Dose (MTD)
The MTD will be defined as the highest dose level where a grade 3 or greater with an attribution score of ≥ 3 develops in ≤ 2 of 6 patients in a dose group within 4 months of the treatment.
9. Laboratory values are not required for this protocol and will not be collected.

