3.2 Enrollment/Randomization

This study will include 8 patient cohorts with 3 patients per cohort. The patients will be enrolled and treated following a Bayesian method permitting precise determination of the therapeutic working-dose while directly controlling the likelihood of an overdose. The method, known as Escalation with Overdose Control (EWOC), has been used to design phase I clinical trials at several cancer centers including the Fox Chase Cancer Center (PA), the Sylvester Comprehensive Cancer Center (FL), and the Winship Cancer Institute (GA) and pharmaceutical companies. EWOC was the first dose-finding procedure to directly incorporate the ethical constraint of minimizing the chance of treating patients at unacceptably high doses. Its defining property is that the expected proportion of patients treated at doses above the MTD is equal to a specified value α , the feasibility bound. This value is selected by the clinician and reflects his/her level of concern about overdosing.

The dose levels for the trial are summarized in Table 1. The dose for the first cohort of 3 patients in the trial will be the dose level 0, previous results indicating this to be a safe dose. The patient accrual will be suspended until the 4 month toxicity evaluation is completed for all previously enrolled patients. The dose for each subsequent cohort of 3 patients will be determined so that, on the basis of all available data and the target highest acceptable toxicity level of 25% DLT, the probability that it exceeds the MTD is equal to a pre-specified value α . In this trial, we set $\alpha = 0.25$ and increase α in small increments until $\alpha = 0.5$, this value being a compromise between the therapeutic aspect of the agent and its toxic side effects. The dose selected for every patient in the trial will be between the minimum dose of 27.5 Gy and the maximum allowable dose of 40 Gy. The trial will be terminated if 3 DLTs are observed in any cohort of 3 patients treated with the lowest dose level. The trial will stop after 24 patients have been enrolled and MTD will be estimated from one of the 6 specified dose levels listed in the Table 1. If no MTD is found because even the highest dose level is still considered under toxic, then the highest dose group will be considered the MTD and expanded to 12 patients.

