6.2 Serious Adverse Events (SAEs)

Any adverse event that results with any of the following outcomes:

- Death;
- A life-threatening experience;
- Inpatient hospitalization or prolongation of existing hospitalization;
- A persistent or significant disability/incapacity;
- A congenital anomaly/birth defect; or
- Other medically important events.

6.3 All adverse events will be reported to the PI and co-investigators.

6.4 Any SAE will be reported to the DSMC in a scheduled summary of toxicities and SAEs at 4 months after completed enrollment of the ongoing dose level/before dose escalation.

6.5 Any death thought to be at least possibly related to treatment will halt the study and will be reported to the DSMC within 24 hours of the investigators knowledge of the event.

6.6 The study may also be halted should the PI feel for any reason there is undo risk to patients with continued dose escalation.

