APPENDIX A – Patient Assessment Timeline

	Baseline	Weekly on RT	1 month	4 months	7 months	10 months	13 months	16 months	19 months	22 months	25 months
H&P	X		X	X	X	X	X	X	X	X	X
Toxicity Assessment		X	X	X	X	X	X	X	X	X	X
MRI	X		X	X	X	X	X	X	X	X	X
HVLT-R	X		X	X	X		X		X		X
MMSE	X		X	X	X		X		X		X
MOS	X		X	X	X		X		X		X
FACT-Br	X		X	X	X		X		X		X
Imaging Response Evaluation			X	X	X	X	X	X	X	X	X

*Assessments may occur within a +/- 3 week window the specified time.

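### The evaluation that clears each cohort may take place up to 3 weeks early, so the next dose can be chosen with up to 17% of the 4-month DLT window unobserved

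*Combined protocol and SAP*

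**What the plan says.** Four sets of statements bear on the timing.

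- **Visits.** Section 3.8.1 item 2 places toxicity assessments at "1 month and 4 months after completion of radiation therapy, and every 3 months thereafter", and adds: "A plus or minus 3 week window will be allowed for follow-up assessments". The footnote to Appendix A says the same for the whole table: "Assessments may occur within a +/- 3 week window the specified time". Neither excepts the 4-month visit.
- **What is counted.** For the MTD, Section 3.8.1 item 8 counts attributable grade 3 or higher events among "patients in a dose group within 4 months of the treatment". The primary analysis in Section 5.3.1 is the toxicity rate at 4 months.
- **What opens the next cohort.** Section 3.2 states: "The patient accrual will be suspended until the 4 month toxicity evaluation is completed for all previously enrolled patients". It places the decision to escalate or de-escalate after every patient in the dose group has completed that assessment. The Precis promises four months of observation of each completed cohort before the dose is raised.
- **DSMC reporting.** Section 6.4 schedules the toxicity and SAE summary "at 4 months after completed enrollment of the ongoing dose level/before dose escalation". Section 7.2.4 asks for a summary every four months from first enrollment and/or before each escalation.

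**The concern.** The gate is defined by completion of a visit, while the DLT count is defined by elapsed time, and the visit window lets the two come apart. A patient seen at the early edge has completed the 4-month evaluation in the sense of Section 3.2 but has not been followed for 4 months. No text asks for a further toxicity check when the full 4 months are reached, and the next scheduled one in Appendix A is at 7 months. The plan therefore allows a dose decision on less follow-up than its Precis promises and its MTD definition uses.

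Cohorts have three patients, so one event not yet seen can change a decision. The example of sequential enrollment in Section 3.2 moves to the next level unless a grade 3 or 4 toxicity has been documented.

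The DSMC summary raises a smaller, separate point. Its date runs from enrollment and the toxicity window from radiation, so on that date the last patient may still be short of 4 months after treatment.

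**Working it through.** **Inputs from the documents.** Visit window ±3 weeks, anchor at completion of radiation, DLT window of 4 months (Section 3.8.1, Appendix A). Target DLT rate 25% (Section 3.2). Eight cohorts of three and a 4-year goal (Precis). Five fractions at 2 to 3 per week (Section 3.3.1).

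**The plan's own figure.** 8 × 3 = 24 reproduces the fixed sample size. Eight cohorts give 7 between-cohort gates. A fixed-size EWOC design has no power formula, and the documents give no priors, so there is no power figure to reproduce and the effect on the EWOC dose or the MTD cannot be computed.

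**Length of the gap.** 4 months = 4 × 30.4375 = 121.75 days. The earliest permitted visit is 121.75 − 21 = day 100.75. The unobserved share is 21 / 121.75 = 17.2%. This counts the DLT window from the last fraction, as item 2 counts the visits; item 8 does not say which fraction it means.

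**Effect at the target rate, p = 0.25.** The documents give no onset pattern, so each line rests on an assumption.

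- Constant hazard: observed rate = 1 − 0.75^(100.75/121.75) = 0.212.
- Uniform onset: observed rate = 0.25 × 100.75/121.75 = 0.207.
- No DLT in three, full follow-up: 0.75³ = 0.422.
- No DLT in three, all visits at the early edge, constant hazard: (1 − 0.2118)³ = 0.490.
- No DLT in three, only the last patient at the early edge: 0.75² × (1 − 0.2118) = 0.443.
- At most 2 DLTs in 6 (the item 8 rule), binomial: 0.831 with full follow-up, 0.886 with all six visits early and constant hazard.

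**Range over onset patterns.** Let s be the assumed share of 4-month DLTs that begin in the last 3 weeks. The observed rate is then 0.25 × (1 − s).

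| s | Observed rate | P(0 of 3), all early | P(0 of 3), last only | Expected DLTs unseen per cohort, all early / last only |
|---|---|---|---|---|
| 5% | 23.8% | 0.443 | 0.429 | 0.04 / 0.01 |
| 30% | 17.5% | 0.562 | 0.464 | 0.23 / 0.08 |
| 50% | 12.5% | 0.670 | 0.492 | 0.38 / 0.13 |

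**How many patients are likely to be short.** Eight observation periods take 8 × 4 = 32 of the 48 months. The remaining 16 months for 24 patients give 16 × 30.4375 / 24 = about 20 days per patient. At that pace, usually only the last patient of a cohort is materially short of 4 months when the cohort clears.

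**DSMC date.** A course runs about 9 days (Mon/Wed/Fri/Mon/Wed) to 14 days (Mon/Thu/Mon/Thu/Mon) from first to last fraction. With an assumed 0 to 14 days from enrollment to first fraction, 4 months after the last enrollment falls 9 to 28 days short of 4 months after that patient's radiation.

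**The case against.** Symmetric visit windows are ordinary, and this one also runs 3 weeks late. The Precis still requires four months of observation, and nothing says an early visit waives it. Detection does not depend on scheduled visits alone: grade 3 or higher nervous system toxicity goes to the PI, each DLT goes to the DSMC, the investigators meet monthly, and MRI may be done at clinical deterioration. Section 3.2 bases each dose on all data accumulated so far, and Section 2.1.2 includes late toxicity, so an event missed at one decision can enter later ones and the final MTD.

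Most of this stands, and it rules out three stronger readings that a reader might infer.

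- *DLTs are under-counted and the MTD is biased upward.* The documents show only that DLTs can be missing at the time of a decision.
- *The late side of the window also loses events.* Section 3.8.1 item 3 classes toxicity as "acute (within 4 months), or chronic (more than 4 months) based on timing after SRS", and item 8 refers to toxicity that develops within the period. Both point to onset rather than visit date. A late visit observes the whole window.
- *The DSMC clock allows early escalation.* Section 3.2 ties the decision to completed assessments, and Sections 6.4 and 7.2.4 also place the summary before escalation. DLTs reach the DSMC individually as well.

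The objection does not remove the early edge. The operative gate in Section 3.2 is completion of a visit that may be early, and Section 3.8.1 item 4 has toxicities recorded at the prespecified assessment points. The safeguards make it more likely that an event between visits is noticed, but none requires a check at 4 months.

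**Conclusion.** The point holds for the early edge of one visit. The gates in Section 3.2 can be met at about day 101 of 122, which conflicts with the observation period in the Precis and the within-4-months count in Section 3.8.1 item 8. The loss falls mainly on the next dose decision. It becomes permanent if the patient is lost, if onset is never dated, or if the patient goes off study, because item 6 does not count a grade 3 event after that point as a DLT and Section 4.6 includes whole brain radiation and patient request among the off-study criteria.

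Its size depends on an onset pattern that has to be assumed. In the likelier case, with only the last patient early, the effect at the target rate is modest; the figures with all three early are a worst case. The DSMC timing is a reporting gap: the scheduled summary may lack the last patient's complete data. This is a cheap correction worth making before accrual, and it does not show that the MTD will be wrong.

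**What to change.** 1. Reconcile Section 3.8.1 item 2 and Appendix A with the Precis. For the cohort-clearing evaluation only, make the window −0/+3 weeks from 4 months after the last fraction. Alternatively, keep ±3 weeks and require a documented toxicity check at the full 4 months whenever the visit was early. Other visits keep their window.
2. Record the onset date of each grade 3 or higher CNS event, and decide whether it falls within 4 months by onset rather than by visit date. Counting everything first recorded at a late visit would stretch the window to about 4.7 months ((121.75 + 21) / 30.4375) for some patients and is not advised.
3. Reword Sections 6.4 and 7.2.4 so that the cohort summary follows the last patient's completed 4-month post-radiation evaluation and precedes the opening of the next cohort.

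The cost is protocol wording, an Appendix A footnote and one date field. Under the −0/+3 option a cohort waits up to 3 weeks longer if its last visit would have been early; the worst case is 7 × 3 = 21 weeks of the 4-year goal. The documented-check option largely avoids an extra visit, though the cohort still should not clear before the check is made.
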